8.2.3. Vital Signs

BP and pulse rate measurements will be assessed either in the sitting position with feet supported (ie, not dangling) or the semi-recumbent/supine position. It is recommended that the same position be used consistently throughout the study duration unless circumstances, eg, hospitalization, dictate otherwise. BP should be obtained using the auscultatory method or via an automated BP device, ensuring use of an appropriately sized cuff on the bare arm and consistent technique of measurement (eg, using the same arm each time). Care should be taken to use the appropriate size BP cuff for the participant's arm circumference as incorrect cuff sizes can lead to falsely elevated BP measurements.

Abnormal readings should be repeated and confirmed.

Blood pressure and pulse rate measurements should be preceded by at least 5 minutes of rest for the participant in a quiet setting without distractions (eg, television, cell phones).

Pulse rate preferably should be obtained using a pulse oximeter, automated BP device, or other pulse measurement device.

Temperature may be determined using oral, tympanic, axillary, or temporal (ie, forehead scan) methods of measurement, as long as the chosen method is used consistently (oral preferred). The method of temperature measurement should be noted in the CRF.

When should it be done:

Vital sign assessments should precede blood draw for clinical laboratory tests.

8.2.4. Electrocardiograms

Standard 12-lead ECGs utilizing limb leads (with a 10 second rhythm strip) should be collected at times specified in the [SoA](#) section of this protocol using an ECG machine that automatically calculates the heart rate and measures PR, QT, and QTc intervals and QRS complex. All 12 lead ECGs should be confirmed by a qualified individual at the institution or use a fully validated automated ECG analysis. All ECGs in a single participant should be analyzed by the same reader. Alternative lead placement methodology using torso leads (eg, Mason-Likar) should not be used given the potential risk of discrepancies with ECGs acquired using standard limb lead placement. All scheduled ECGs should be performed after the participant has rested quietly for at least 10 minutes in recumbent or semi-recumbent position and before blood draws or vital signs.

At each time point (see [SoA](#)) except screening and EOT, 3 consecutive ECGs (ie, triplicate ECGs) will be performed at approximately 2 minutes apart to determine the mean QTcF interval. ECG assessments should precede blood collection for clinical laboratory tests. When coinciding with blood sample draws for PK, plan the timing of ECG well so that the PK collection afterwards can be around the intended time.

If a) a postdose QTcF interval remains ≥ 60 ms from the baseline **and** is >450 ms; or b) an absolute QT value is ≥ 500 ms for any scheduled ECG for greater than 4 hours (or sooner, at the discretion of the investigator); or c) QTcF intervals get progressively longer, the participant should undergo continuous ECG monitoring until QTcF values from 2 successive ECGs fall below the threshold value that triggered the repeat measurement. In addition, if verified QTcF values continue to exceed the criteria above, immediate correction for reversible causes including electrolyte abnormalities, hypoxia and concomitant medications for drugs with the potential to prolong the QTcF interval should be performed.

A cardiologist should be consulted if QTcF intervals do not return to less than the criteria listed above after 8 hours of monitoring (or sooner, at the discretion of the investigator). If in that timeframe the QTcF intervals rise above the threshold values, the study intervention will be held until the QTcF interval decreases to below the threshold values. Participants may resume study intervention at the current dose level or next lower dose level after discussion

with the sponsor. If at any time a participant has a QTcF interval >515 ms or becomes symptomatic, the participant will be discontinued from study treatment. Additional triplicate ECGs may be performed as clinically indicated.

In some cases, it may be appropriate to repeat abnormal ECGs to rule out improper lead placement as contributing to the ECG abnormality. It is important that leads be placed in the same positions each time in order to achieve precise ECG recordings. If a machine-read QTc value is prolonged, as defined above, repeat measurements may not be necessary if a qualified medical provider's interpretation determines that the QTcF values are in the acceptable range.

ECG values of potential clinical concern are listed in [Appendix 7](#).

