2.3.1. Risk Assessment

Potential risks of clinical significance for sasanlimab are provided in the sasanlimab IB.

Study Intervention: PF-07265028

Potential Risk of Clinical Significance	Summary of Data/Rationale for Risk	Mitigation Strategy
Immune-related toxicity	The potential overlapping risks are based on the sasanlimab IB and nonclinical studies for PF-07265028.	
 Guidelines for treatment interruption/dose reductions and discontinuation in case toxicities, and guidelines for steroid treatment implementation are incorporated in Section 6.5.1.
ISRs	The potential risks of sasanlimab administered with PF-07265028 are based on the sasanlimab IB and nonclinical studies for PF-07265028.	
 Participants should be monitored for serious and nonserious AEs, including ISRs, following administration of sasanlimab (in Parts 1B and 2A). When appropriate, at the discretion of the investigator, a participant with an ISR may be referred for a dermatological consultation and skin biopsy may be obtained for future examination of the ISR. If injection site reaction is noted, site tolerability assessments should continue until the symptoms resolve. Refer to Section 8.2.7.
Gastrointestinal (mucosal erosion, epithelial degeneration/regeneration) with accompanying clinical signs of emesis and diarrhea.	The potential risks are based on nonclinical toxicology data for PF-07265028 in mice and monkeys.	
 Participants will be monitored for gastrointestinal toxicity. At the discretion of the investigator therapeutic and prophylactic supportive care may be considered. Dose reductions/ interruptions and discontinuations are permissible. Potential of dosing with food.
Marrow (increased myeloid to erythroid ratio)	The potential risks are based on nonclinical toxicology data for PF-07265028 in mice and monkeys.	
 Participants will be monitored for hematologic toxicity. At the discretion of the investigator therapeutic and prophylactic supportive care may be considered. Dose reductions/ interruptions and discontinuations are permissible.
Increased hemodynamics (increased heart rate and/or blood pressure)	Identified in a single dose cynomolgus monkey telemetry study of PF-07265028.	
 Participants will have serial vital signs performed.

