Hematologic	Continue at the same dose level.	Continue at the same dose level.	Withhold dose until toxicity is Grade ≤ 2 , or has returned to baseline, then resume treatment at the same dose level.	Withhold dose until toxicity is Grade ≤ 2 , or has returned to baseline, then reduce the dose by 1 level and resume treatment or discontinue at the discretion of the investigator.

Specific GI toxicities potentially related to PF-07265028 should be managed according to the dose modifications described in [Table 9](#).

090177e198aafefApproved\Approved On: 22-Nov-2021 20:52 (GMT)

Table 9. Dose Modifications for PF-07265028 Related GI Toxicity

Grade 1	Grade 2	Grade 3*	Grade 4
Continue at the same dose level and, institute standard of care supportive measures at the discretion of the investigator.	Continue at the same dose level and institute standard of care supportive measures at the discretion of the investigator. If recurrent and intolerable, withhold dose until toxicity is Grade ≤ 1 , or has returned to baseline, then resume treatment at the next lower dose level	Withhold dose until toxicity is Grade ≤ 1 , or has returned to baseline, then resume treatment at the same dose level or reduce the dose by 1 level at the discretion of the investigator. If recurrent, withhold dose until toxicity is Grade ≤ 1 , or has returned to baseline, then reduce the dose by 1 level.	Withhold dose until toxicity is Grade ≤ 1 , or has returned to baseline, then reduce the dose by 1 level and resume treatment, or discontinue at the discretion of the investigator. If recurrent, permanently discontinue treatment

*Nausea, vomiting, or diarrhea must persist at Grade 3 despite optimal supportive care to require dose modification.

Note: Cycle will not be extended to cover for the missing dose.

Note: For management of GI iRAEs see [Appendix 3 Section 10.3](#).

Note: Participants with confirmed Hy's Law must be discontinued.

Table 10. Dose Modifications for PF-07265028 Related QTcF Prolongation

QTcF >480 ms \leq 500 ms	QTcF >500 ms	Recurrent QTcF >500 ms	QTcF >500 ms or >60 ms change from baseline, and Torsade de pointes or polymorphic ventricular tachycardia or signs/symptoms of serious arrhythmia

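### Section 8.2.4 starts continuous ECG monitoring on uncorrected QT under trigger (b) but ends it, and judges the later steps, on QTcF

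*Protocol*

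**What the plan says.** Protocol Section 8.2.4 (Electrocardiograms) lists three conditions, any of which puts a participant on continuous ECG monitoring:

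- (a) "a postdose QTcF interval remains ≥ 60 ms from the baseline" and is also above 450 ms;
- (b) "an absolute QT value is" at least 500 ms on any scheduled ECG for more than 4 hours, or sooner if the investigator so decides;
- (c) "QTcF intervals get progressively longer", with no number attached.

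Monitoring then runs "until QTcF values from 2 successive ECGs fall below the threshold value that triggered the repeat measurement". The steps that follow are also worded in QTcF and refer back to the same criteria: correction of reversible causes, the consult ("A cardiologist should be consulted if QTcF intervals do not return to less than the criteria listed above after 8 hours of monitoring"), and the rule for holding and resuming study intervention. The section ends with a separate rule that discontinues study treatment if QTcF exceeds 515 ms at any time.

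Elsewhere, the numeric limits are all QTcF: exclusion criterion 12 (above 470 ms at screening), the DLT definitions in Section 4.3.3.2, Table 10 in Section 6.5 (including its column for "Recurrent QTcF >500 ms"), Appendix 7, the categories in Protocol Section 9.3.5.1, and SAP Table 2 and SAP Appendix 1. Two sentences say only QTc without naming the correction (the note to Table 10 and the remark on machine readings in Section 8.2.4). Neither sets a limit of its own.

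**The concern.** Trigger (b) is the only numeric QT limit in either document set on an uncorrected interval, and no reason is given. Its release test uses a different measure. For a participant who enters monitoring under (b), the threshold that triggered is a QT number, yet the value compared with it is QTcF. The two agree only at 60 bpm. Away from that rate, starting and stopping monitoring are not governed by one rule, and the later steps inherit the problem because they point back to the same criteria.

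This is a safety-monitoring rule in a first-in-human study. The ECG machines report both QT and QTc, so two sites could act differently on the same tracing, each with support from the text.

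**Working it through.** The plan gives no figure of its own to reproduce, so the check converts between the two measures and then sees what the neighbouring rules cover.

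**Inputs.** Trigger (b): QT 500 ms (Section 8.2.4). Trigger (a): rise of at least 60 ms and QTcF above 450 ms (Section 8.2.4). Highest QTcF admitted at screening: 470 ms (Section 5.2, criterion 12). Discontinuation: QTcF above 515 ms (Section 8.2.4). Dose action: QTcF above 500 ms (Table 10). Default correction: Fridericia (Section 9.3.5.1). The heart rates are assumed for illustration.

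**Step 1, conversion.** QTcF = QT / RR^(1/3), with RR = 60 / heart rate. For example, at 50 bpm 500 / 1.2^(1/3) = 470.5, and at 80 bpm 500 / 0.75^(1/3) = 550.3.

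| Heart rate (bpm) | RR (s) | QTcF when QT = 500 ms | QT when QTcF = 500 ms |
|---|---|---|---|
| 50 | 1.200 | 470.5 | 531.3 |
| 60 | 1.000 | 500.0 | 500.0 |
| 70 | 0.857 | 526.4 | 475.0 |
| 80 | 0.750 | 550.3 | 454.3 |
| 100 | 0.600 | 592.8 | 421.7 |

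**Step 2, trigger against release.** At 50 bpm, QT from 500 to just under 531 ms fires (b) while QTcF lies between 470.5 and 500 ms. The release test, QTcF below 500, is then met at the outset. At 80 bpm, (b) does not fire until QTcF reaches 550 ms, while release needs QTcF below 500 ms, which is QT below 454 ms. Above 60 bpm there are therefore QTcF values over 500 ms at which (b) is silent.

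**Step 3, cover from trigger (a).** In the range of interest, (a) fires at baseline + 60 ms.

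- Baseline 440: 440 + 60 = 500, so nothing from 500 ms upward escapes (a).
- Baseline 450: values from 500 to just under 510 escape.
- Baseline 460: values from 500 to just under 520 escape.
- Baseline 470: values from 500 to just under 530 escape.

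A gap therefore needs a baseline above 440 ms. The upper figure of 470 ms assumes that the pre-dose baseline is no higher than the screening limit.

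**Step 4, cover from the 515 ms rule and Table 10.** Anything above 515 ms leads to discontinuation of study treatment whichever trigger applies. That leaves 500-515 ms, or 500 to baseline + 60 when the baseline is below 455 ms. Within that band, Table 10 already calls for dose action on drug-related QTcF above 500 ms.

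**Step 5, heart rate needed.** QT stays below 500 ms at a given QTcF when the heart rate exceeds 60 × (QTcF / 500)^3. At QTcF 500 this is 60 bpm. At QTcF 515 it is 60 × 1.03^3 = 65.6 bpm. No unusual tachycardia is required.

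**The case against.** The strongest reply is that (b) is loose wording. Sections 8.2.4(a) and (b) look like the usual pair of a change from baseline and an absolute value, and both the protocol and SAP categorical tables pair the two in that way for QTcF. The follow-on sentences treat all three triggers as QTcF criteria, and the remark on machine readings speaks of QTc being prolonged as already defined. On that reading, trigger and release already agree. This is plausible, but no passage says it, and a site has to apply the words as printed.

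A reader might go further and infer that a participant with QTcF of, say, 501-529 ms would go unmanaged. The documents do not support that. Values above 515 ms fall under the discontinuation rule, and Table 10 acts from just above 500 ms. What can be lost is continuous monitoring.

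A reader might also infer that (b) contradicts Appendix 7 and the SAP categories. Appendix 7 lists findings that may qualify as adverse events, and the SAP categories are for tabulation. Neither says when monitoring starts.

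Nor should the heart-rate signal in Section 2.3.1 be pressed. It comes from a single-dose monkey telemetry study. Section 2.2.7 calls the haemodynamic changes modest and reports no ECG change, QT included.

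Investigators may act sooner under (b) and may repeat ECGs. That eases the consequences but does not say which measure applies.

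**Conclusion.** The firm defect is inside Section 8.2.4: trigger (b) is stated in QT, while its release test and the later steps are stated in QTcF. The mismatch affects the result at any heart rate other than 60 bpm and does not depend on how many participants it would touch.

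The practical gap is small and confined to continuous monitoring. It needs a baseline QTcF of about 441-470 ms, a rise of less than 60 ms, a heart rate above roughly 60-66 bpm and trigger (c) not met, and it lies mainly at QTcF 500-515 ms. The error in the other direction, monitoring that starts when its release test is already met, occurs below 60 bpm and removes no protection.

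The size rests on the Fridericia formula and on illustrative heart rates. The documents give no distribution of heart rate or baseline QTcF, so the number of participants affected cannot be estimated. If (b) was meant as QTcF, the gap disappears and only the wording needs correcting.

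**What to change.** Reconcile the passages in Section 8.2.4. State explicitly whether trigger (b) is uncorrected QT or QTcF. Then express the trigger, the release test, the reversible-cause step, the cardiology consult and the hold-and-resume rule on that one measure. If uncorrected QT is intended, give the reason. Check the result against Table 10 and the 515 ms rule so that the monitoring and dosing rules can be followed together. Which measure or threshold is clinically right is for the sponsor and its cardiac advisers; none is proposed here.

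The cost is a wording change in one section. The machines specified in Section 8.2.4 already supply heart rate, QT and QTc, so no new data collection is needed, and neither the sample size nor the planned analysis changes.

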Dose levels that have cleared the DLT period in Part 1 may be expanded up to 10 participants PF-07265028 administered as monotherapy or in combination sasanlimab at or below the MTD. Expansion of dose levels will be based on evolving clinical data (including safety, PK, and PD) to explore activity and help identify the RDE of the monotherapy and/or combination in Part 2.

Please see below for intra-participant dose escalation rules and rules for crossover from Part 1A to Part 1B.

- To minimize the risk that an individual participant may be exposed to a sub-therapeutic dose, intra-participant dose escalation of PF-07265028 in Part 1 to the maximal dose level that has previously been determined to be safe (based on BLRM) may be allowed if the protocol required safety assessments for the previous treatment cycle have been performed and as follows:
 1. Participant has completed 2 cycles of treatment at the current dose level; or if disease progression occurs.
 2. No Grade ≥ 3 treatment-emergent toxicities were experienced at the participant's current dose level.
 3. If a clinical rationale is provided by the investigator and approved by the sponsor.
- In Part 1A (monotherapy dose escalation) participants with SD after 2 cycles of treatment, and additionally participants with a RECIST response of PR or CR, who then experience PD, may rollover to the combination cohort regardless of prior PDx status.

Participants in Part 1 must have recently obtained archival tumor tissue available (collected within 6 months prior to screening). If the archival sample is older than 6 months, the participant must consent to undergo a fresh pre-treatment biopsy during the screening period. If a new biopsy represents a significant safety risk in the opinion of the investigator, the participant may be considered for enrollment with archival samples only after discussion with the sponsor.

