Reduce the dose of drug by one level without interruption of dosing. Following dose reduction, the drug dose may be resumed at the previous level in the next cycle if the QTcF has decreased to within 30 ms of baseline or <450 ms but subject must be monitored closely for QT prolongation for the first cycle at the increased dose.	Withhold dose for up to 14 days. If QTcF returns to within 30 ms of baseline or <450 ms within 14 days, resume and reduce by 1 dose level.	Permanently discontinue treatment if QTcF >500 ms recurs despite appropriate dose reduction and correction/elimination of other risk factors (eg, serum electrolyte abnormalities, concomitant QT prolonging medication)	Permanently discontinue treatment

Note: For all episodes of QTc prolongation, regardless of grade, check electrolyte (potassium, calcium, and magnesium) levels and correct any abnormalities. If possible, stop any medications that may prolong the QT interval (see [Section 8.2.4](#) for management of QTc prolongation).

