6.5.2. Dose Reductions

No dose reductions are permitted for sasanlimab.

Following dosing interruption or cycle delay due to treatment-related toxicity, the PF-07265028 dose may need to be reduced when treatment is resumed.

No specific dose adjustments are recommended for Grade 1 or 2 treatment-related toxicity. However, investigators should always manage their participants according to their medical judgment based on the particular clinical circumstances.

Participants experiencing recurrent and intolerable treatment-related Grade 2 toxicity may resume dosing at the next lower dose level once recovery to Grade ≤ 1 or baseline is achieved.

Dose reduction of PF-07265028 by 1 and, if needed, 2 dose levels will be allowed depending on the type and severity of toxicity encountered. Participants requiring more than 2 dose reductions will be discontinued from the treatment and entered into the Follow-up phase, unless otherwise agreed between the investigator and the sponsor. All dose modifications/adjustments must be clearly documented in the participant's source notes and CRF.

Once a dose has been reduced for a given participant, all subsequent cycles should be administered at the reduced dose level, unless further dose reduction is required. Intraparticipant dose re-escalation is not allowed.

Participants experiencing a DLT may resume dosing at the next lower dose level (if applicable) once adequate recovery is achieved, and in the opinion of the investigator and sponsor, the participant is benefiting from therapy.

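### Two QTcF dosing rules contradict each other: Table 10 against Section 8.2.4 above 515 ms, and Table 10 against Section 6.5.2 on returning to the previous dose

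*Protocol*

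**What the plan says.** Three places in the protocol govern dosing of PF-07265028 after QTcF prolongation.

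- **Section 8.2.4 (Electrocardiograms).** "If at any time a participant has a QTcF interval >515 ms or becomes symptomatic, the participant will be discontinued from study treatment". The rule has no exception for a first episode. The same section separately describes a temporary hold, so discontinuation here means stopping treatment.
- **Section 6.5, Table 10, column for QTcF above 500 ms.** The dose is withheld for up to 14 days. Then: "If QTcF returns to within 30 ms of baseline or <450 ms within 14 days, resume and reduce by 1 dose level". The column has no upper bound. Table 10 stops treatment permanently only if QTcF above 500 ms recurs despite dose reduction, or if there is torsade, polymorphic ventricular tachycardia or signs or symptoms of serious arrhythmia.
- **Section 6.5, Table 10, column for QTcF above 480 and up to 500 ms.** The dose is lowered one level. Then: "Following dose reduction, the drug dose may be resumed at the previous level in the next cycle", provided QTcF has recovered and the participant is watched closely.
- **Section 6.5.2 (Dose Reductions).** "Once a dose has been reduced for a given participant, all subsequent cycles should be administered at the reduced dose level", the only stated exception being a further reduction. It adds: "Intraparticipant dose re-escalation is not allowed".

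A note under Table 10 points to Section 8.2.4 for managing QTc prolongation. Section 8.2.4 does not point back to Table 10, and no text ranks the three.

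**The concern.** These are safety rules in a first-in-human trial and should give one answer for one ECG. Above 515 ms, an investigator who follows Table 10 as written re-doses a participant whom 8.2.4 says must come off treatment. An investigator who follows 8.2.4 denies the participant a restart that Table 10 provides. After a reduction for a smaller prolongation, an investigator who uses Table 10's permission raises a dose that 6.5.2 forbids raising. At stake are participant safety and clean protocol compliance, not the statistical analysis.

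**Working it through.** The protocol gives no figure to reproduce. The check applies each rule to the same participant. Thresholds and dose levels come from Table 10, Section 8.2.4 and Table 7; the ECG values are illustrative.

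**Case 1: first QTcF above 515 ms, asymptomatic, no arrhythmia.** Baseline 440 ms, first QTcF 520 ms, falling to 465 ms on Day 5 of the hold.

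- Rise: 520 − 440 = 80 ms.
- Table 10 restart limit: 440 + 30 = 470 ms. Since 465 ≤ 470 and Day 5 is within 14 days, the restart condition is met.

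| Rule | Outcome |
|---|---|
| Table 10, above 500 ms | Withhold, then resume one level lower |
| Section 8.2.4, above 515 ms | Treatment already discontinued |

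Both cannot be followed. Neither rule is conditioned on baseline, so this can arise at any eligible baseline. Section 6.5.2 adds to the tension: a participant with a DLT may restart at the next lower level if benefiting, with no exception for QTcF above 515 ms.

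**Case 2: return after a reduction.** Baseline 430 ms, dose 125 mg, QTcF 485 ms, reduced to 80 mg. QTcF is 445 ms before the next cycle.

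- Rise: 485 − 430 = 55 ms, below the 60 ms trigger in 8.2.4, so that section plays no part.
- Recovery: 445 < 450, so Table 10's condition for return is met.

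| Rule | Outcome |
|---|---|
| Table 10, above 480 and up to 500 ms | 125 mg permitted next cycle |
| Section 6.5.2 | 80 mg in all later cycles |

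Size of the disputed step on the Table 7 levels:

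- 80 to 125 mg: 125/80 = 1.5625, an increase of 56%.
- 50 to 80 mg: 80/50 = 1.60, an increase of 60%.
- 25 to 50 mg: 50/25 = 2.00, an increase of 100%.

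**Could Section 4.1.1 supply the missing permission?** It allows intra-participant escalation in Part 1 under conditions that include "Participant has completed 2 cycles of treatment at the current dose level; or if disease progression occurs". A return in the very next cycle does not in general meet that, and Part 2 is not covered.

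**The case against.** **Table 10 only permits the return; it does not require it.** This stands. A site that keeps the reduced dose complies with both texts, so a reader who infers that Case 2 forces a breach either way goes too far. The breach occurs only when the permission is used.

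**The sponsor decides.** Section 6.3.1 has the sponsor determine the dose, which is dispensed through the IRT. Section 8 requires immediate discussion with the sponsor on whether a participant continues or stops. A reader might infer that sites would act differently on the same ECG; with one sponsor involved throughout, that is less likely. But Section 8 also rules out protocol waivers, and discussion does not say which written rule the sponsor should apply.

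**The texts can be read together.** The Table 10 note leads to 8.2.4, so the 515 ms stop could be taken as a cap inside the column above 500 ms. Equally, Table 10 could be the specific exception to the general ban in 6.5.2. Both readings are sensible, and the fix builds on the first. The protocol states neither.

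**Further conflicts a reader might infer.** Table 10 says "Reduce the dose of drug by one level without interruption of dosing" for QTcF above 480 and up to 500 ms, while 8.2.4 says "If in that timeframe the QTcF intervals rise above the threshold values, the study intervention will be held". This is a contradiction only if the undefined thresholds include the rise of at least 60 ms. If they mean only the 500 ms value, Table 10 also withholds above 500 ms. The 60 ms trigger also requires the rise to persist, and a daily dose is lost only if the elevation lasts until that dose is due. Nor do the differing restart doses conflict: 8.2.4 allows the current or next lower level, and Table 10's reduction lies within that choice.

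**Conclusion.** Two contradictions stand: discontinuation against withhold-and-resume for a first, asymptomatic QTcF above 515 ms without arrhythmia, and permitted return against barred re-escalation after a reduction for QTcF above 480 and up to 500 ms. Both come from current protocol text. The second involves a dose increase of 56% to 100% on the provisional dose levels. How often either would arise is unknown; the monkey telemetry in Section 2.2.7 showed no QT change.

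A reader might infer that DLT counts or the dose-escalation model would shift, because Cycle 1 dose delivery feeds the 75% rule. The documents do not establish this:

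- Grade 3 QTcF prolongation that persists after correction of reversible causes, and any Grade 4 prolongation, is already a DLT under Section 4.3.3.2. The choice of dosing rule would matter only for an event not otherwise a DLT, with delivered dose falling on different sides of 75%.
- The disputed return comes in a later cycle, outside the Cycle 1 DLT window, and SAP Section 5.2 groups participants by initial dose.

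No effect on endpoints, DLT calls or the model is claimed. This is a minor to should-fix wording correction, worth making because it concerns participant safety.

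**What to change.** 1. In Table 10, limit the withhold-and-resume column to a first QTcF above 500 and up to 515 ms, and add the 8.2.4 discontinuation above 515 ms to the table.
2. Settle re-escalation in one of two ways. Either add to the ban in Section 6.5.2 the words *except as permitted in Table 10 for QTcF prolongation*, or delete the return to the previous level from Table 10.

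The first change keeps the stricter of the two existing rules. The second is a clinical choice for the sponsor; either option removes the contradiction. The cost is protocol wording in the next amendment, with no extra procedures or participants.
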